We will undertake a prospective, interventional, non-randomised, implementation study of mPOCT for COVID-19 in adults presenting to University Hospital Southampton NHS Foundation Trust. A brief validation and training phase will be followed by the post-implementation phase where patients will be recruited and tested at the point-of-care using the QIAstat-Dx Respiratory SARS-CoV-2 Panel. We will initially test patients suspected of COVID-19 based on current PHE case definitions and then progress to testing all patients with ARI as the outbreak becomes more widespread in the UK and the risks of admitting patients to hospital with unsuspected COVID-19 are high. Clinical and infection

control teams will be informed of these results in real time. The control group will consist of patients who were tested for SARS-CoV-2 by laboratory PCR but not recruited to the study during the same time period. This allows us to have a comparable control group as the outbreak progresses and hospital pathways change, as opposed to a pre-implementation group which predominantly is expected to consist of community-based patients tested in hospital for containment reasons. Only anonymised, routinely collected hospital data will be obtained for the control group. Outcome measures will be by assessed by retrospective case note analysis and will include: time to result, time in isolation facilities, detection of COVID-19 cases not initially suspected (based on current PHE case definition), antibiotic use, antiviral use, length of hospital stay, ward closures and hospital resource use. Multivariate analysis will be used to control for the effect of confounding variables between the groups.

Potential benefits to patients and the NHS

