1. To assess the clinical impact of mPOCT for respiratory viruses including SARS-CoV-2 on outcomes measures including: time to test result, time in COVID-19 assessment cohort areas, time to definite ward move, length of stay in hospital, use of antibiotics, use of antivirals, ward closures, and hospital resource use, in adults hospitalised with ARI.

2. To assess the implementation feasibility of mPOCT for COVID-19.

3. To assess the ease-of-use, reliability and real-world diagnostic accuracy of the QIAstat-Dx SARS-2-CoV assay, , using respiratory samples prospectively collected from adults presenting to hospital with ARI, compared to the reference standard of PHE laboratory RT-PCR for SARS-CoV-2.

6. Recruitment and Study Processes

Overview

This is a non-randomised, controlled, implementation study of mPOCT for respiratory viruses including COVID-19 with prospective recruitment for participants in the intervention phase. The intervention consists of testing respiratory samples from patients at the point-of-care using the QIAstat-Dx Respiratory SARS-CoV-2 Panel. In the contemporaneous control group, routinely collected data on outcomes in patients tested for COVID-19 using laboratory RT-PCR, including time to test result. In the intervention phase patients will be tested using the QIAstat-Dx Respiratory SARS-CoV-2 Panel with results delivered immediately to the clinical and infection control team and outcome and diagnostic accuracy data collected retrospectively. A brief validation phase will precede the intervention phase. Study processes that patient-participants undergo in intervention phase are summarised in Figure 1.

[figure not shown]

Figure 1: Participant flow through the study

POCT = point-of care test

*if lacks capacity to consent, participant's consultee may be substituted here

Control group

Patients (≥18 years old) presenting to hospital with ARI who have been tested for SARS-CoV-2 during the same time period as part of standard clinical care (but not included in the intervention) via University Hospital Southampton NHS Foundation Trust (UHS) will be identified via (laboratory) information management system and select clinical data will be obtained by electronic records including age, sex, co-morbidity, observations, blood test results, length of hospital stay, and time to test result. Consent is not obtained for these patients, and only anonymised data already collected as part of routine clinical care will be used.

Screening

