For potential participants with infection control concerns, consent and consultee declaration forms may be marked with initials and signatures written with a finger or stylus on an electronic device that is subsequently cleaned (e.g. an iPad or similar), rather than paper. In these situations, participants and/or their consultees are still provided with a paper copy of any signed forms.

Validation phase

The study intervention starts with the validation/verification phase which will last approximately 1-2 weeks. The QIAstat-Dx Respiratory SARS-CoV-2 Panel with be validated using the specific control material from Zeptopetrix (NATRVP-QIA) which contains targets for all non SARS-CoV-2 pathogens on the panel, as per the manufacturers recommendations and using their suggested protocols. The SARS-CoV-2 assays will be validated using control material provided by Qiagen (single stranded DNA fragments homologous to the SARS-CoV-2 genes – the E-gene and Rdp gene - targeted by the assays) and from SARS-CoV-2 positive patient samples. The validation will take place in the Clinical Research Facility laboratory under BSL2 conditions and will also test the diagnostic accuracy of the assays on control material placed in molecular media compared to viral transports media (see below).

Intervention phase

Once the analysers have been fully validated using control material and the research staff adequately trained in use of the QIAstat-Dx and fully PPE trained, the validation phase will end and move in the intervention phase. Providing the validation phase is successful (and/or CE marking has been granted) the study will move in the intervention phase where all patients presenting to UHS with ARI will be approached (including those fulfilling the PHE case definition for suspected COVID-19). The intervention recruitment phase will last up to 6 months.

Procedures

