Table 1. Optional additional tests for those testing positive for SARS-CoV-2 or any endemic coronavirus

Inclusion / exclusion criteria

Inclusion criteria:

- Is a patient in ED, AMU, HDU, GICU, medical wards, or another location within Southampton General Hospital, University Hospital Southampton NHS Foundation Trust (UHS)

- Aged ≥18 years old

- Can be recruited to the study within 24 hours of presentation to hospital

Plus:

- Has acute respiratory illness (ARI)*

OR

- Does not have ARI but is a suspected case of COVID-19 according to the current PHE case definition OR

- Does not have ARI or fulfil the PHE case definition of a suspected case but testing for SARS-CoV-2 is considered necessary by the responsible clinical team

*An episode of acute respiratory illness is defined as an acute upper or lower respiratory illness (including rhinitis, rhino-sinusitis, pharyngitis, pneumonia, bronchitis and influenza-like illness) or an acute exacerbation of a chronic respiratory illness (including exacerbation of COPD, asthma or bronchiectasis). For the study, acute respiratory illness as a provisional, working, differential or confirmed diagnosis must be made by a treating clinician.

Exclusion criteria:

- Not fulfilling all the inclusion criteria

- Declines nasal / pharyngeal swabbing

- Consent declined or consultee consent declined
- Already recruited to the study in the last 14 days

Further inclusion / exclusion notes

Concurrent, prior, or subsequent enrolment in another study is not necessarily an exclusion criterion; this is at the discretion of the chief investigator and will be assessed on a case-by-case basis. Local R&D measures including a "12 week exemption form" must be in place and agreed with the chief investigator that may facilitate co-enrolment in other studies.

The inclusion of pregnant women is permitted in the study. No additional risk is perceived to pregnant women or their offspring by any of the study procedures. No additional data collection or monitoring is therefore anticipated in this group. It may be especially important to include pregnant women in COVID-19 research, as infection with influenza is associated with worse outcomes in pregnancy [11]. Data on abnormalities at birth or congenital defects and other serious adverse events are collected and may be reportable (see relevant section on Safety).

Staff testing

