Non-hospitalised hospital staff members may be included in the intervention phase of the study, if they satisfy the other inclusion & exclusion criteria. The same consent and study procedure processes are followed. However, their results will not be included in analyses of most outcome measures, with the exception of time to result. Days away from work may be used as an additional outcome measure.

Participant Withdrawal

A participant, or their consultee where a participant lacks capacity, may decide to withdraw from the study at any time, without giving reason, and with no detriment to their medical care or legal rights.

The chief investigator may withdraw a patient from the study in the interests of participant safety or the integrity of the research study, or on the advice of the sponsor's representative (R&D department).

Any patient, or their consultee where a patient lacks capacity, who is withdrawing from the study has the options withdraw and have data and/or samples collected so far retained, or withdraw and have their data and/or samples destroyed (but signed consultee declaration forms, minimal personal identifiable information to record the withdrawal, and any completed point-of-care test result will be retained). Although the study procedures are very brief, if a patient loses capacity after enrolment but before the study procedures are completed, consultee consent must be sought to continue with any study procedures, or the participant must be withdrawn.

A note to file would normally be sufficient to record any withdrawal.

7. Outcomes

Primary outcome

• The primary outcome measure is the time from COVID-19 test being requested to the result being available to clinical teams.

Secondary Outcomes

- The time from presentation to hospital to COVID-19 test result
- Time spent in COVID-19 assessment cohort area
- Time to definitive ward move
- Number of bed moves •
- Duration of hospitalisation •
- Number and proportion of clinically unsuspected COVID-19 positive patients detected •
- Proportion of patients treated with antibiotics
- Proportion of patients treated with single doses or brief courses (<48 hours) of antibiotics •
- Duration of antibiotic use, days
- Proportion of all influenza antiviral use occurring in influenza positive patients •
- Proportion of all influenza antiviral use occurring in influenza negative patients •
- Time from admission to influenza antiviral commencement

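### A between-group difference in clinically unsuspected COVID-19 cases cannot be read as extra detection by mPOCT, because controls are only patients whom standard care had already tested

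*Protocol*

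**What the plan says.** Protocol section 7 (Secondary Outcomes) lists "Number and proportion of clinically unsuspected COVID-19 positive patients detected". It names no denominator and does not restrict the outcome to one group.

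Section 2 (Methods) gives the meaning of unsuspected. Among the outcome measures it lists "detection of COVID-19 cases not initially suspected (based on current PHE case definition", so suspicion is judged by the PHE definition, not by whether a clinician ordered a test. The same paragraph promises multivariate analysis for confounding between the groups. Section 11 then prescribes chi-square tests between groups for binary data. Its own example is a detection outcome (influenza cases detected), and it makes no exception for this one.

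On the controls, section 2 says "The control group will consist of patients who were tested for SARS-CoV-2 by laboratory PCR but not recruited to the study". Section 6 (Control group) takes patients with ARI who were "tested for SARS-CoV-2 during the same time period as part of standard clinical care (but not included in the intervention".

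On who enters the intervention group, the protocol says two things. Section 2: "We will initially test patients suspected of COVID-19 based on current PHE case definitions and then progress to testing all patients with ARI". Section 6 (Intervention phase): "the study will move in the intervention phase where all patients presenting to UHS with ARI will be approached". The inclusion criteria in section 6 give three entry routes with no staging: ARI; no ARI but meeting the PHE definition; and a third route for patients who have no ARI and do not "fulfil the PHE case definition of a suspected case but testing for SARS-CoV-2 is considered necessary by the responsible clinical team".

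**The concern.** Sections 2 and 4 give the reason for this outcome: testing by case definition will miss infected patients, and routine mPOCT will find them before they cause spread on the wards. The quantity of interest is the number of cases found that standard care would have missed.

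The control group cannot supply the other side of that comparison. A missed case is one that standard care did not test, and an untested patient is never a control. Covariate adjustment cannot recover patients who lie outside the sampling frame. The intervention group, by contrast, is meant to include patients tested on account of ARI alone. If the default analysis is followed, a difference produced by who was tested could be reported as evidence that mPOCT finds missed cases.

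The disagreement between sections 2 and 6 adds a second problem. If recruitment begins with patients who meet the PHE definition, those participants cannot be unsuspected. The rate over the whole group then depends on when recruitment widened.

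**Working it through.** **No figure to reproduce.** The protocol gives no expected rate, effect, power or event count for this outcome, and section 8 calls the prevalence highly speculative. The only input taken from the document is 500 patients per group. Everything else below is assumed.

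**Check 1: selection alone.** Let s be the share of a group outside the PHE definition and p the positivity among those patients. Take all 500 as the denominator; this is also an assumption, since none is stated. The expected rate is s × p. Set p equal in the two groups, so that the test has no effect. P(sig) is the approximate probability that a two-sided 5% comparison of 500 v 500 is significant.

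| p | s, intervention | s, control | Rates (s × p) | P(sig) |
|---|---|---|---|---|
| 0.10 | 0.60 | 0.10 | 6% v 1% (30 v 5 patients) | 0.99 |
| 0.10 | 0.60 | 0.30 | 6% v 3% (30 v 15) | 0.63 |
| 0.10 | 0.60 | 0.60 | 6% v 6% | 0.05 |
| 0.10 | 0.30 | 0.60 | 3% v 6% (15 v 30) | 0.63 |
| 0.02 | 0.60 | 0.10 | 1.2% v 0.2% | 0.475 |
| 0.30 | 0.60 | 0.10 | 18% v 3% | above 0.99 |

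The spurious difference can be large, can be absent, and can even reverse if more of the controls lie outside the definition. With equal shares it disappears. Even then, the cases that standard care left untested are still not in the control group, so the comparison says nothing about them.

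**Check 2: recruitment timing, if section 2 governs.** Let w be the share of the 500 recruited after widening and u the share of those outside the definition. Leave the third entry route aside. The rate over all 500 is w × u × p. With u = 0.60 and p = 0.10:

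- w = 0.25: 0.25 × 0.60 × 0.10 = 1.5% (7.5 of 500)
- w = 0.50: 3.0% (15 of 500)
- w = 0.75: 4.5% (22.5 of 500)
- w = 1.00: 6.0% (30 of 500)

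Timing alone gives a fourfold range. Over u from 0.30 to 0.60, p from 0.02 to 0.30 and w from 0.25 to 1, the rate runs from 0.15% to 18%.

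If the denominator is instead the participants outside the definition, the rate is (w × u × p) / (w × u) = p. The switch date cancels. What remains is the variation of p over the outbreak, which is why reporting by calendar period is needed as well.

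**Check 3: the third entry route.** A positive patient enrolled by this route counts as unsuspected under the PHE-based meaning, although the clinical team wanted a test. These patients have no ARI, while section 6 limits controls to patients with ARI. On that wording they can add to the intervention numerator and have no counterpart among the controls.

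**The case against.** The strongest reply is that no sentence names this outcome for a between-group test. Objective 1 in section 5 omits it. The same list in section 7 contains outcomes that exist only in the intervention group, such as run failures, ease of use and assay accuracy, so being listed does not imply a comparison. Choice of denominator is commonly left to an SAP, which is not at hand. This stands in part: the missing denominator is not in itself the fault. But section 2 places the outcome beside the adjusted comparison of groups, and section 11 states a general rule for binary data with no exception. As written, the default is comparative.

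Several stronger readings are tempting, and the protocol does not support them:

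- That the control rate is zero by construction. Suspicion is defined by the PHE definition, and the inclusion criteria foresee clinicians testing outside it. Tested controls can be unsuspected positives.
- That the outcome cannot answer any question. How many positives outside the definition mPOCT finds is directly observable in the intervention group.
- That the reported proportion is diluted by a known factor. That would need a fixed denominator of 500, which is stated nowhere.
- That the third entry route inflates detection among ARI patients. It admits only patients without ARI.
- That the rate certainly depends on a switch date. This follows only if section 2 governs over section 6.

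The moving PHE definition is not a defect either. Whether a patient was suspected under the rules in force on the day is the operational question that section 4 raises. It only requires that the version be recorded.

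**Conclusion.** The point holds in a limited form. The default analysis would compare a group tested largely on account of ARI with a group selected because standard care had tested them, and a difference between the two is not an estimate of extra detection. The size is unknown because the shares outside the PHE definition are not given. With 10% positivity assumed in both groups, it runs from no spurious difference (equal shares) to 6% v 1% (shares of 60% v 10%). Nothing in the design makes the shares equal.

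Separately, sections 2 and 6 contradict each other on staging. If section 2 governs, the rate over the whole intervention group could vary fourfold with an unstated switch date, under the assumptions shown. The descriptive question in the intervention group remains answerable. One secondary outcome is affected and the primary outcome is not, but the correction is cheap and prevents a misleading claim.

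**What to change.** - State that this outcome is reported descriptively in the intervention group only, with no between-group test.
- Use as denominator the participants who did not meet the PHE definition in force when they presented.
- Record entry route and definition version at enrolment.
- Report by calendar period, and show positives from the third entry route (no ARI, test wanted by the clinical team) separately.
- Reconcile sections 2 and 6 on whether recruitment is staged and, if it is, record the date on which it widened.

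It would be tempting also to exclude anyone who had a clinician-ordered test before enrolment. That is not advised. Classification would then depend on whether the clinician or the research team acted first within the 24-hour recruitment window, and it would replace the protocol's own meaning of unsuspected.

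The cost is a change of outcome wording and an enrolment entry for route and definition version. The price is a smaller denominator, hence a less precise proportion, and no comparative claim for this outcome.

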The impact of mPOCT for COVID-19 in hospitals is likely to be large given the very prolonged delay in obtaining laboratory RT-PCR results for suspected cases and the requirement for enhanced infection control procedures including the use of negative pressure side rooms for patients and full PPE for staff, while awaiting results. As most patients with suspected COVID-19 are expected to test negative (at least in the early part of the outbreak) the use of mPOCT is expected to lead to the avoidance of using negative pressure side room or early de-isolation for COVID-19 negative patients and the avoidance or early de-escalation of enhanced PPE for staff. In addition there may be additional benefits of mPOCT such as early cessation of unnecessary antibiotics, early directed antivirals for influenza and early appropriate discharges for certain patients. The early detection of SARS-CoV-2 in patients presenting to hospital with ARI who were not clinical suspected (based on the current PHE case definition) will prevent widespread nosocomial transmission and ward closures. Early, accurate identification of hospitalised COVID-19 positive patients will also allow enrolment into trials of investigational antiviral therapeutics and vaccines, and will allow early directed antiviral therapy once it becomes available.

Alignment with global research priorities

Laboratory testing for COVID-19 by RT-PCR is the current standard diagnostic strategy for all countries. Laboratory testing capacity was rapidly exceeded in China due to the huge volume of cases leading to alternative diagnostic strategies including CT scanning of the chest as a surrogate test for viral pneumonia. Due to the limited laboratory capacity and prolonged turnaround for results alternative diagnostic strategies are urgently needed for COVID-19 across the globe. This study will demonstrate the feasibility and clinical impact of mPOCT for COVID in hospitals as well as studying real-world diagnostic accuracy of the QIAstat-Dx Respiratory SARS-Cov-2 assay.

5. Aim and Objectives

Aims

To evaluate the clinical impact, implementation feasibility and real-world diagnostic accuracy of routine mPOCT for respiratory viruses including SARS-CoV-2 in adults presenting to hospital with suspected COVID-19 and/or ARI.

Objectives

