Participants will be enrolled and assigned a unique participant identification number consecutively. Respiratory samples will be collected from patients by an appropriately trained member of research staff wearing full PPE as defined by UHS infection prevention and control policy. A combined nose and throat swab, and if available, a lower respiratory tract sample (sputum, or for patients in critical care units BAL or ET secretions) will be obtained and tested. Samples will be immediately placed in a sigma MWMM (molecular medium) or similar tube (containing detergent and Guanidine thiocyanate) to rapidly and completely inactivate any virus present (within 1 minute). The sample will then be loaded in the test kit and tested on the QIAstat-Dx analyser housed in the acute area. The result will be available in around 1 hour and will be delivered to the clinical and infection control teams as soon as results are available. The system will be de-contaminated prior to and after use in accordance with the manufactures instructions.

All participants may be approached for a finger-prick blood test with the FebriDx (RPS, FI., USA) and a second nose and throat swab in viral transport media (participants may opt out of one or both of these).

Patients testing positive for COVID-19 and for 'seasonal' non-COVID-19 coronaviruses may be approached for additional respiratory samples and/or blood samples for additional virological, serological and host response analysis at various time points (see Table 1 and laboratory analysis plan).

Participant involvement end date

Participant involvement in the study is considered ended once their last physical interaction with the research team has finished, although some retrospectively collected outcome measures will still be collected from records after this time (e.g. 30 and 60 day mortality). For patients testing negative for coronaviruses this is expected to be the same day as enrolment. For patients testing positive for a coronavirus, this may be the same day as enrolment if no further samples are collected, or the date of the last additional samples acquired (see Table 1). Participant withdrawal is discussed separately.

Day 0 (enrolment day) +/- 72 hours	Day 14 (+/- 4 days)	Day 28 (+/- 4 days)
Blood test (max 22ml)	Blood test (max 22ml)	Blood test (max 22ml)
Additional nose & throat swabs +/- lower respiratory sample	Nose & throat swabs	Nose & throat swabs

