- Duration of influenza antiviral use, days and doses •
- Proportion of patients with ICU or RHDU admission •
- Proportion readmitted to hospital within 30 days •
- In hospital, 30 and 60 day mortality •
- Reliability (proportion of run failures), ease-of-use scores [12], and implementation feasibility • assessment (narrative) of QIAstat-Dx Respiratory SARS-CoV-2 Panel, used at the point-of-care.

Sensitivity, specificity, positive predicted value, negative predictive value, percentage positive agreement, percentage negative agreement, percentage overall agreement, and overall diagnostic accuracy of QIAstat-Dx SARS-CoV-2 assay (as part of QIAstat-Dx Respiratory SARS-CoV-2 Panel) compared to laboratory PCR using the PHE RdRP assay.

All outcomes are measured for the duration of hospitalisation or up to 30 days (whichever is shortest) unless specified otherwise and include medication (antibiotics and antivirals) that patients are discharged home with.

Exploratory Outcomes

Changes in viral load over time (kinetics) in upper and lower respiratory tract samples for COVID-19 positive patients.

Antibody levels and changes over time (kinetics) in blood for COVID-19 positive patients and patients positive for other 'seasonal' non COVID-19 coronaviruses.

Presence or absence of MxA at presentation in fingerpick whole blood (as tested by FebriDx) in patients with and without COVID-19.

Host response (transcriptomic) at presentation and over time in patients with and without COVID-19. Time to administration of experimental antiviral (if and when available)

8. Sample size

Proposed sample size

The sample size of 500 patient-participants is chosen pragmatically based on the current availability of the QIAstat-Dx Respiratory SARS-CoV-2 Panel test kits. The manufacturer has agreed for us to purchase this number. The kits are in high demand given the epidemic situation with limited supply.

500 patients would give a clinically meaningful assessment of a range of clinical outcome measures including time to results, time in COVID-19 assessment cohort areas, time to definitive ward move, and duration of hospitalisation. It will also allow a robust assessment of the reliability and ease-of-use of the platform. Aiming to recruit more than 500 patients may delay analysis and dissemination of results of this study and subsequent policy changes the study results may bring, especially in a fast-paced outbreak situation.

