Accepting that the prevalence of COVID-19 during the study is highly speculative at present, and so formal samples size calculation for diagnostic accuracy studies are not possible, testing 500 patients will allow us to make an ongoing assessment of the real-world diagnostic accuracy of the QIAstat-Dx Respiratory SARS-CoV-2assay compared to the current reference standard of laboratory PCR testing using the PHE RdRP assay.

The control group will be 500 patients for an adequate comparison.

9. Data collection

Demographic and clinical data will be collected for all patients at enrolment including: age, sex, ethnicity, smoking status, vaccination status, co-morbidities, medication use, symptoms, duration of illness prior to hospitalisation, observations (pulse rate, respiratory rate, blood pressure, oxygenation status), laboratory results, radiology results, antimicrobial and antiviral use prior to hospitalisation and provisional diagnosis. Data will be recorded on a Case Report Form, which we intend to be electronic (ALEA). Once patients have been discharged or after 30 days (whichever is soonest), clinical data will be collected retrospectively from electronic and physical case notes including: use of antivirals, duration of antivirals, time from assessment to antiviral use, use of side room facilities, time from assessment to isolation facility use, time to clinical stability, duration of supplementary oxygen use, duration of hospitalisation, complications including ICU and RHDU admission, representation and readmission to hospital within 30 days, final diagnosis and mortality. The number of diagnostic tests and procedures performed will also be recorded and data will also be collected on the turnaround time of respiratory virus test results in each group.

10. Data Management

The subjects' anonymity will be maintained. The study team will keep a log of each subject's name, hospital ID number, date of birth, and unique participant trial number. The participant details will be recorded on the secure NHS Edge system in a similar manner, including NHS number. This participant trial number is used on documents after screening to maintain confidentiality. Documents that are not anonymous (e.g. signed informed consent forms) will be maintained separately, in strict confidence.

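### The antibiotic-use outcome counts courses begun before the swab, which shrinks any effect of the test and can mix in a baseline difference between the non-randomised groups

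*Protocol*

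**What the plan says.** Section 7 names the outcome as "Proportion of patients treated with antibiotics". The window for the whole list is set in the same section: "All outcomes are measured for the duration of hospitalisation or up to 30 days (whichever is shortest) unless specified otherwise". The antibiotic item specifies nothing different, so the window opens at hospitalisation, not at sampling.

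Section 6 (inclusion criteria) admits intervention patients under the condition "Can be recruited to the study within 24 hours of presentation to hospital". Section 6 (Procedures) adds that "The result will be available in around 1 hour" once the sample is loaded. Controls, also in section 6, are patients "who have been tested for SARS-CoV-2 during the same time period as part of standard clinical care", and no limit from presentation to test is stated for them.

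The baseline list in section 9 includes "antimicrobial and antiviral use prior to hospitalisation and provisional diagnosis". It does not name antibiotics given in hospital before the swab. Section 11 plans chi-square tests for binary outcomes and, in general terms, multivariate adjustment for confounding, with no covariates named.

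**The concern.** A patient given a first dose in the emergency department before being approached for the study is counted as treated whatever the test later shows. The same holds for a patient whose community course continues on admission. These patients form a block of events that the intervention cannot change.

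Two things follow. The block dilutes any real effect on later prescribing. Also, because allocation is not randomised and the two groups may be tested at different times after arrival, the block may differ in size between groups, and an unadjusted comparison would attribute that to the test. Antibiotic use is one of the clinical impacts named in Objective 1 (section 5). The mechanism that section 4 expects is "early cessation of unnecessary antibiotics", which an ever-treated proportion cannot register once a dose has been given.

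**Working it through.** The protocol gives no antibiotic rate, effect size or power to reproduce; section 8 bases the sample size on kit supply. The calculation below is therefore an illustration.

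**Inputs**
- 500 per group (section 1).
- Two-sided 5% level (assumed; none is stated).
- f, the share already on antibiotics before the swab (assumed, 0 to 0.8).
- q, the share of the remaining patients who start later (assumed; 60% in controls and 50% with the point-of-care test).

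**Dilution.** The ever-treated proportion is p = f + (1 − f)q. With the same f in both groups, the difference is (1 − f)(q0 − q1).

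Power uses the normal approximation with pooled variance under the null: Φ{[d − 1.96√(2p̄(1 − p̄)/n)] / √[(p0(1 − p0) + p1(1 − p1))/n]}.

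At f = 0.6:
- p0 = 0.6 + 0.4 × 0.6 = 0.84; p1 = 0.6 + 0.4 × 0.5 = 0.80; d = 0.04.
- The two standard errors are 0.02430 (null) and 0.02427 (alternative).
- Φ[(0.04 − 0.0476)/0.02427] = Φ(−0.314) = 0.377.
- Among the 500 × 0.4 = 200 per group not yet treated, the difference is still 0.10 and power is 0.520.

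| f | Ever treated, control v test | Difference | Power, all 500 per group | Power, not-yet-treated only |
|---|---|---|---|---|
| 0 | 60% v 50% | 10 points | 89% | 89% |
| 0.2 | 68% v 60% | 8 points | 75% | 81% |
| 0.4 | 76% v 70% | 6 points | 57% | 69% |
| 0.6 | 84% v 80% | 4 points | 38% | 52% |
| 0.8 | 92% v 90% | 2 points | 20% | 29% |

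For 80% power on the all-patient measure, the number per group rises from 388 at f = 0 to 1447 at f = 0.6.

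With a larger assumed effect (50% v 35% later starts), f = 0.6 gives 80% v 74% ever treated. Power is 62% for all patients and 86% among the 200 per group not yet treated.

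**Imbalance with no test effect.** With the same q in both groups, the spurious difference is (f1 − f0)(1 − q). At q = 0.5:

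| f in the two groups | Ever treated | Difference | Unadjusted test significant |
|---|---|---|---|
| 40% v 45% | 70% v 72.5% | 2.5 points | about 14% of trials |
| 40% v 50% | 70% v 75% | 5 points | about 42% |
| 50% v 60% | 75% v 80% | 5 points | about 47% |
| 60% v 70% | 80% v 85% | 5 points | about 55% |

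**Data available to correct for this.** The pre-hospital antimicrobial item covers the community-course case for enrolled patients, and the enrolment item on medication use may show current antibiotics. Controls are not enrolled. Their extraction list in section 6 is open-ended but names neither antibiotic use nor its timing.

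**The case against.** The strongest reply is that this is a pragmatic implementation study. The proportion of all patients treated is the effect of the testing policy as delivered, including tests that come too late to matter. On that view dilution is part of the answer and not a bias. This stands, and it is why the all-patient proportion should not be demoted.

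Second, the next two items in section 7, brief courses under 48 hours and duration of antibiotic use, can register stopping after a result. This also stands in part: the protocol is not blind to early cessation, although both items also count doses given before the swab.

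Third, adjustment is promised, and its covariates may be set out in an analysis plan that is not at hand. That is fair, but the outcome and its window are fixed in the protocol, and no item for in-hospital antibiotics before the swab is named for the adjustment to use.

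Fourth, a restricted analysis has its own weakness. A patient still untreated many hours after arrival is probably at lower risk than one untreated on arrival, and controls have no stated limit from presentation to test. This stands and shapes the fix.

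A reader might go further and infer that the antibiotic comparison is invalid, or that it will produce a false positive in about half of trials. The documents do not support this. They show no imbalance, and the rejection rates above need an assumed one and no adjustment.

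**Conclusion.** The point holds as a limited, inexpensive improvement to a secondary outcome. On the protocol's own definitions, antibiotics given before the swab count as events, and any effect of the test on later starts is reduced by the factor (1 − f). That direction does not depend on the assumed rates. The size does: f, the later start rates and any difference in f between groups are all absent from the documents, so the power and rejection figures are illustrations and not properties of this trial. Confounding through f is possible because the groups are not randomised and their times to test are not aligned, but it is not demonstrated. Restricting to patients not yet treated gains power at every non-zero f tried, yet at f = 0.6 with a 10-point effect it reaches only 52%. The primary outcome in section 7 is unaffected.

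**What to change.** - Keep the all-patient proportion as the pragmatic comparison.
- Extract the time of the first antibiotic dose relative to a common index time (test request or sampling, defined the same way in both groups), controls included. Result time is unsuitable as the index, because the intervention changes it.
- Add an analysis of new antibiotic starts after the index time among patients not yet treated.
- Adjust or stratify the all-patient, brief-course and duration comparisons for antibiotic status at the index time.
- Adjust all of these analyses for time from presentation to the index time, because the 24-hour limit is stated only for the intervention group.

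The cost is a change to the outcome and analysis wording, one derived variable, and modest extra extraction of prescribing times, much of which the duration outcome needs anyway. The restricted analysis has fewer patients, and some selection from differing index times will remain after adjustment.
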